The dose levels to be tested will initially be 40, 80, 160, 300, and 600 mg orally once per day. Additional dose levels (e.g., intermediate levels or larger or smaller doses) or dosing schedules (e.g., twice daily) may be studied at the discretion of the Safety Review Committee (SRC) based on their review of safety data and any PK, pharmacodynamics, and efficacy data. Intra-patient dose escalation will be allowed for subjects enrolled in the Phase 1 portion once subsequent dose levels have been deemed safe by the SRC. Phase 1 subjects continuing treatment during the Phase 2 expansion will be offered the opportunity to be randomly assigned to one of the Phase 2 doses, if considered appropriate by the investigator. Subjects must have demonstrated compliance as well as a safe and favorable toxicity profile to participate in intra-patient dose escalation.

The AR phenotype and AR levels of each subject's disease will be evaluated pre-treatment and on study based on analyses of circulating tumor DNA, circulating tumor cells, banked biopsy tissues, or on-study tumor biopsies.

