#### **4.1.3. Phase 1 Intra-Patient Dose Escalation**

Phase 1 subjects who have advanced beyond their DLT evaluation window will be offered the opportunity to escalate to a subsequent dose level that has been deemed safe by the SRC. Once the SRC has chosen the two doses for the Phase 2 expansion, Phase 1 subjects continuing treatment will be offered the opportunity to be randomly assigned to one of these Phase 2 doses, if considered appropriate by the Investigator. Subjects must have demonstrated compliance as well as a safe and favorable toxicity profile to participate in intra-patient dose escalation.

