### **8.3.8. Time Period and Frequency for Collecting AE and SAE Information**

Investigators will seek information on AEs at each subject contact. All AEs will be collected and recorded in the subject's medical record and on the Adverse Event eCRF as follows:

- From signing of ICF until first dose of study treatment: All SAEs, AEs due directly to study-related procedures/assessments, and AEs leading to subject/study discontinuation.
- From first dose of study treatment through 30 days after the last dose of study treatment OR initiation of subsequent anti-cancer therapies, whichever occurs first: All AEs and SAEs.
- Ongoing AEs/SAEs that are definitely, probably, or possibly related to study drug, should be followed until resolution or stabilization to  $\leq$  Grade 2, or returned to baseline status.

See Section 8.3.9 for instructions on recording AEs and SAEs, including abnormal laboratory values; pre-existing medical conditions; hospitalization; and disease progression, relapse, or disease-related death.

For each AE recorded on the Adverse Event eCRF, the Investigator will make an assessment of seriousness (Section 8.3.6), severity (Section 8.3.4), and causality (Section 8.3.5).

SAEs are required to be reported by the Investigator to the Sponsor immediately (i.e., no more than 24 hours becoming aware of the event). See Section 8.4 for reporting instructions.

Investigators are not obligated to actively seek AE or SAE collection after conclusion of the study participation. However, if the Investigator learns of any SAE, including a death, at any time after a subject has been discharged from the study and he/she considers the event to be reasonably related to the study drug or study participation, the Investigator must promptly notify the Sponsor.

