## **9. STATISTICS**

### **9.1. Sample Size Determination**

#### **9.1.1. Phase 1 Dose Escalation**

In the Phase 1 portion of the study, 5 dose levels are planned to be evaluated in a dose escalation/de-escalation manner using a BOIN design to determine the MTD. The target DLT rate for the MTD is  $\phi = 0.3$  and the maximum sample size is approximately 27 across the 5 planned dose levels, with a maximum of 12 subjects treated per dose level.

The first 2 dose levels will use an accelerated titration design with a cohort size of 1 and will expand to a cohort size of 3 upon the first instance of a DLT, an existing Grade 2 condition that worsens to Grade 3, or a new Grade 2 AE. When this occurs then all higher dose levels will use a cohort size of 3 and follow the escalation/de-escalation/ elimination rule described in Section 9.5.1.

The dose levels to be tested will initially be 40, 80, 160, 300, and 600 mg orally once per day. Additional dose levels (e.g., intermediate levels or larger or smaller doses) or dosing schedules (e.g., twice daily) may be studied at the discretion of the SRC based on their review of safety data and any PK, pharmacodynamics, and efficacy data. If this does occur, then the number of dose levels of the BOIN design and total number of subjects included in the study will increase accordingly while using the same BOIN design for the escalation/de-escalation/elimination rules.

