## **9.2. Populations for Analysis**

The DLT-evaluable Population is defined as all subjects in the Phase 1 Dose Escalation part of the study who receive ONCT-534 and either complete the 28-day DLT observation period or discontinue the study early due to a DLT. Subjects will be grouped by the dose received.

The Safety Population is defined as all subjects who receive at least one dose of ONCT-534. Subjects will be grouped by the ONCT-534 dose received at study entry.

The Efficacy-evaluable Population is defined as all subjects who receive ONCT-534 and complete at least one post-treatment disease assessment and do not discontinue due to clinical evidence of disease progression without documentation prior to obtaining post-treatment disease assessment. Subjects will be grouped by dose received.

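### Safety tables group Phase 1 subjects by entry dose throughout, so adverse events arising after an upward dose change are counted under the lower starting dose

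*Combined protocol and SAP*

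**What the plan says.** Section 9.2 defines one Safety Population for the whole study, namely everyone who receives at least one dose. It fixes the grouping with no limit by phase or time: "Subjects will be grouped by the ONCT-534 dose received at study entry".

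The design lets that dose change:
- Once past the DLT window, a Phase 1 subject "will be offered the opportunity to escalate to a subsequent dose level that has been deemed safe by the SRC" (section 4.1.3; section 1.1 agrees: "Intra-patient dose escalation will be allowed for subjects enrolled in the Phase 1 portion once subsequent dose levels have been deemed safe by the SRC").
- After the Phase 2 doses are chosen, "Phase 1 subjects continuing treatment will be offered the opportunity to be randomly assigned to one of these Phase 2 doses" (section 4.1.3).
- Table 2 in section 6.2.2 allows reductions for toxicity.

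AEs are collected "From first dose of study treatment through 30 days after the last dose of study treatment", or until subsequent anti-cancer therapy if that comes first (section 8.3.8). Treatment may run to Week 108 (section 6.2).

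On outputs, section 9.5.5 lists AE summaries by System Organ Class, Preferred Term, CTCAE grade and relationship, plus an exposure summary. Section 9.4 groups summaries by dose level in Phase 1 and by expansion dose level in Phase 2, and leaves further detail to a SAP. Section 9.8 promises subject listings. For the Efficacy-evaluable Population, section 9.2 says only: "Subjects will be grouped by dose received".

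**The concern.** Safety and tolerability at escalating doses is a primary Phase 1 objective (section 3.1). The BOIN rules use only the first 28 days, so longer-term tolerability by dose has to be read from the AE tables. A subject who starts at 40 mg, escalates and then has an event at the higher dose appears as an event in the 40 mg column. If risk rises with dose, the lower-dose columns can overstate toxicity. The higher-dose column, meanwhile, lacks events and exposure that did occur at that dose. Both effects tend to flatten the apparent dose-toxicity relation.

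The columns may be very small. "The first 2 dose levels will use an accelerated titration design with a cohort size of 1" (section 9.1.1), and the subjects at those levels have the most dose levels above them.

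A related gap concerns efficacy. The grouping dose is not defined there for a subject who changed dose. Section 9.5.2 lets Simon Stage 1 include subjects who had the same dose in Phase 1, without saying whether someone who reached that dose by escalation qualifies.

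**Working it through.** The plan states no figure on this point, so there is none to reproduce. The check has three parts.

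**1. Which results can be affected.** Under section 4.1.3, escalation is offered only after the subject's own DLT window. DLTs used for dose finding are those in the first 28 days (section 9.5.1), and the DLT-evaluable Population has its own grouping by dose received (section 9.2). DLT rates, BOIN decisions and the MTD are therefore untouched. The escalation offer is confined to Phase 1 subjects, so it does not alter the comparison of subjects who enter in Phase 2. What remains is the Phase 1 safety tables after Day 28.

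**2. How far one event moves a column.** Dose levels 1 and 2 hold one subject each, or three after expansion.
- One post-escalation event turns 0/1 into 1/1.
- In a column of three it turns 0/3 into 1/3, with an exact (Clopper-Pearson) 95% CI of 0.8% to 90.6%.

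The chance of at least one misplaced event among k escalators, each with independent risk r at the higher dose, is 1 − (1 − r)^k. Both k and r are assumptions.

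| r | k = 0 | k = 1 | k = 3 |
|---|---|---|---|
| 10% | 0 | 10% | 1 − 0.90³ = 27% |
| 20% | 0 | 20% | 1 − 0.80³ = 49% |
| 40% | 0 | 40% | 1 − 0.60³ = 78% |

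The k = 1 column simply restates the assumed risk.

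**3. How much follow-up could be affected.** This is an upper bound for the most exposed subject, the first at 40 mg. Assume his own 28 days, then 28 days for one 80 mg cohort, with no gaps before the 80 mg level is deemed safe. The earliest change is then about Week 8.

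| Treated for (assumed) | Weeks after the change | Share |
|---|---|---|
| 24 weeks | 24 − 8 = 16 | 16/24 = 67% |
| 48 weeks | 48 − 8 = 40 | 40/48 = 83% |
| 108 weeks | 108 − 8 = 100 | 100/108 = 93% |

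Subjects who start at higher levels have fewer levels to move to. Those at the highest level tested have none.

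**The case against.** Entry-dose grouping is a stated and defensible choice. It keeps subjects in the group in which they started. A table by dose at onset has its own bias, because "Subjects must have demonstrated compliance as well as a safe and favorable toxicity profile to participate in intra-patient dose escalation". Suppose 6 subjects who entered at a dose have risk p and are pooled with 3 escalators at half that risk. The pooled rate is (6p + 3p/2)/9, so 20%, 40% or 60% becomes 17%, 33% or 50% (assumed figures). This stands, and it is why the entry-dose table should be kept.

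The SAP may add what is missing. That is true, and no separate SAP text is supplied. But section 9.2 is not silent: it fixes a grouping rule, and following it produces the result described.

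Other planned outputs help. Listings allow tracing and may suffice for a one-subject column, but they give no summary of events and time by dose. Section 9.6 correlates PK with safety, but scheduled PK sampling ends at Week 12 (section 8.1.9).

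Three stronger readings are tempting, and the documents do not support them:
- A reader might infer that the MTD or the choice of Phase 2 doses is compromised. The MTD is not, as shown above. The SRC reviews cumulative safety, PK, pharmacodynamic and efficacy data (section 10.1.4), and nothing ties its choice to these tables alone.
- A reader might infer that a dose changer will sit in one column for safety and another for efficacy. The efficacy wording is ambiguous; it does not say that the dose differs from the entry dose.
- A reader might take the 93% bound as typical. It describes one best-case subject treated to Week 108 and says nothing about the average column.

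**Conclusion.** The point holds in a limited form. The entry-dose rule, applied to the whole study, places AEs that arise after an upward change under the lower starting dose, and the supplied text specifies no summary that shows them by dose at onset. This can blur the descriptive Phase 1 dose-toxicity tables beyond Day 28. The direction stated, overstated toxicity in lower-dose columns, assumes that subjects take up the offer and that risk rises with dose. The size cannot be derived, because uptake, event risks and treatment duration are not given. It ranges from nothing without uptake to one event reversing a one-subject column. No decision rule or hypothesis test is shown to change. It is a cheap improvement of low to moderate severity.

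**What to change.** Keep the entry-dose tables. For Phase 1 subjects, add to the SAP:

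1. An AE summary by actual dose at onset, showing the number of subjects and the time at each dose. Use counts rather than percentages or rates in very small columns. Show Phase 1 subjects assigned to a Phase 2 dose separately from the Phase 2 cohorts.
2. An entry-dose AE table with data cut at the first intra-patient escalation or assignment to a higher Phase 2 dose. Do not cut at a toxicity-driven reduction: follow-up would then end because of toxicity, which is informative.

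Also state in the SAP which dose defines the efficacy group of a subject who changed dose, and whether a subject who reached a Phase 2 dose by escalation counts towards Simon Stage 1 under section 9.5.2.

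The cost is SAP wording and programming. AE onset and dosing dates are already needed for the summaries in section 9.5.5, and no dose or clinical rule changes. State the downsides with the tables: a subject may appear in more than one column; escalators are selected for good tolerance, which affects the onset-dose table and also makes the cut in the second table selective; and late toxicity from an earlier dose, including after a reduction, may be attributed to the current dose. Showing the tables side by side lets the reader judge these effects.

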### Study Objectives and Endpoints

The primary objectives of Phase 1 are to assess the safety, tolerability, and DLT of ONCT-534 at escalating doses in subjects with R/R mCRPC and to determine the MTD to inform the 2 dose levels or schedules to be tested in Phase 2. The SRC will evaluate ONCT-534 safety, preliminary efficacy, PK, and pharmacodynamics and select the 2 dose levels or schedules to be studied in Phase 2. Secondary objectives will include assessing the preliminary antitumor activity and PK of ONCT-534.

The primary objectives of Phase 2 are to assess the safety and tolerability of ONCT-534, to compare the 2 dose levels or schedules of ONCT-534 and select the optimal dose for further study, and to assess the preliminary antitumor activity of ONCT-534, based on reduction of prostate-specific antigen (PSA), objective response rate (ORR), complete response rate, duration of response (DOR), radiographic DOR, and progression free survival based on the Prostate Cancer Working Group 3 and Response Evaluation Criteria in Solid Tumors version 1.1 response and progression criteria. Secondary objectives will include correlating antitumor activity of ONCT-534 with AR phenotype and assessing the pharmacodynamics of ONCT-534.

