### Study Procedures

At specific timepoints as outlined in the Schedule of Assessments (Table 1), subjects will undergo assessments/procedures including providing informed consent, interviews, and testing to determine eligibility, disease assessments by computed tomography scan and bone scan,

electrocardiogram, blood tests for hematology, clinical chemistry, PSA levels, ONCT-534 PK, and biomarkers.

Throughout the conduct of the study, subjects will be asked to report concomitant medications and AEs and will have their disease reassessed.

[figure not shown]

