### 1.3. Schedule of Assessments

**Table 1: Schedule of Assessments**

Protocol Section ↓	Study Day/Week →	Screening	D0	D1	D14	D15	D28/W4	W6	W8	W12	W16	W20	W24	Q12W	W108 a	EOT a
	Visit Window (Days) →	-28 to -1			±4		±4	±4	±7	±7	±7	±7	±7	±7	±7	
8.1.1	Eligibility assessments	X														
8.1.2	Physical examination	X	X		X		X	X	X	X	X	X	X	X	X	X
8.1.3	Weight; vital signs	X	X		X		X	X	X	X	X	X	X	X	X	X
8.1.4	12-Lead Electrocardiogram	X	X		X			X		X					X	X
8.1.5	Clinical chemistry	X			X		X	X	X	X	X	X	X	X	X	X
8.1.6	Prostate-specific antigen	X					X		X	X	X	X	X	X	X	X
8.1.7	Clinical hematology; coagulation	X			X		X	X	X	X	X	X	X	X	X	X
8.1.8	Urinalysis	X					X			X			X	X	X	X
6.2.1	ONCT-534 administration in clinic		X	X	X	X	X		X	X						
8.1.9	Blood for pharmacokinetics	X	X	X b	X	X b	X		X	X						
8.1.10	Blood for biomarkers	X					X			X					X	X
8.1.11	Tumor biopsy (encouraged but optional)	X								X						
8.2	CT, chest/abdomen and pelvis c	X								X			X	X	X	
8.2	Bone scan c	X								X			X	X	X	
8.3	Adverse events	X	X	X	X	X	X	X	X	X	X	X	X	X	X d	X d
6.3	Concomitant medications	X	X	X	X	X	X	X	X	X	X	X	X	X	X	X

CT = computed tomography; D = day; EOT = End of Treatment; Q12W = every 12 weeks; W = week.

a EOT Visit at 108 weeks, or if subject discontinues prior to Week 108.

b D1 and D15 pharmacokinetic sample must be collected 24 ± 2 hours from the ONCT-534 dose on D0 and D14, respectively.

c Confirmatory scan(s) required at least 4 weeks after partial response or complete response is first documented.

d All subjects will be contacted 30 + 7 days after their last dose of ONCT-534 for a final safety interview.

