#### Primary Objectives:

- To assess the safety and tolerability of ONCT-534.
- To compare 2 dose levels or schedules of ONCT-534 and select the optimal dose for further study.
- To assess the preliminary antitumor activity of ONCT-534.

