### **8.1.12. End of Treatment and Off-study Assessments**

Subjects who complete the study to the Week 108 visit should have the assessments performed as indicated in the Schedule of Assessments in Section 1.3. If the subject stops treatment prior to Week 108, an End of Treatment Visit should be performed as soon as practical, ideally within 72 hours.

A safety interview will be completed 30 days (+7 days) after the last dose of ONCT-534 for all subjects who discontinue treatment (either at Week 108 or Early Termination) for AEs and concomitant medications associated with serious adverse events (SAEs) that are definitely, possibly, or probably related to ONCT-534.

Every effort should be made to document disease progression that occurs after stopping treatment with ONCT-534 and the next systemic treatment administered.

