### 9.5.4. Analysis of the Antitumor Endpoints

Evaluation of prostate cancer response to treatment (RECIST v1.1 and PCWG3) is described in [Appendix 2](#).

The objective response rate (ORR) is defined as the proportion of efficacy-evaluable subjects with a response to treatment (defined as CR or PR). The number, percentage, and exact 95% CI will be presented.

The CR Rate is defined as the proportion of efficacy-evaluable subjects with a CR to treatment. The number, percentage, and exact 95% CI will be presented.

The duration of response (DOR) is defined as the time (in months) between initial response (CR or PR) and the date of first disease progression, relapse, or death for efficacy-evaluable subjects.

DOR will be analyzed using Kaplan-Meier methods. Further details on censoring rules will be described in the SAP.

The progression-free survival (PFS) is defined as the time (in months) between first study treatment dose date and the date of first disease progression or death from any cause. PFS will be analyzed using Kaplan-Meier methods. Further details on censoring rules will be described in the SAP.

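### ORR and CR rate leave treated subjects with no post-treatment disease assessment out of the denominator, so ORR is overstated relative to all treated subjects whenever such a subject is left out and anyone responds; the CR rate is overstated only if someone has a CR

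*Combined protocol and SAP*

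**What the plan says.** Section 9.5.4 says that ORR "is defined as the proportion of efficacy-evaluable subjects with a response to treatment", with response meaning CR or PR, and that the CR rate "is defined as the proportion of efficacy-evaluable subjects with a CR to treatment". Each is to be reported with an exact 95% CI.

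Section 9.2 sets two conditions for the efficacy-evaluable population beyond receiving ONCT-534. The subject must have at least one post-treatment disease assessment, and must be among those who "do not discontinue due to clinical evidence of disease progression without documentation prior to obtaining post-treatment disease assessment". The same section defines an all-treated set, the Safety Population, but no section assigns it to ORR or CR rate.

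The Synopsis (Study Objectives and Endpoints) says that Phase 2 antitumor activity will be assessed "based on reduction of prostate-specific antigen (PSA), objective response rate (ORR), complete response rate", among other measures. Section 3.2 lists as a further Phase 2 primary objective: "To compare 2 dose levels or schedules of ONCT-534 and select the optimal dose for further study".

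On timing, the Synopsis (Study Procedures) refers to "disease assessments by computed tomography scan and bone scan". In Table 1 the first on-treatment CT and bone scan are at Week 12. The end-of-treatment column, whose footnote reads "EOT Visit at 108 weeks, or if subject discontinues prior to Week 108", has no scan. Section 8.1.12 adds: "Every effort should be made to document disease progression that occurs after stopping treatment with ONCT-534".

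**The concern.** Membership of the denominator depends on what happens after treatment starts. The second condition in Section 9.2 removes, in so many words, subjects who stop because they are getting worse clinically and have no documented progression. These are treatment failures in all but paperwork, and under this definition they disappear from the rate.

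The schedule makes such losses plausible. Under Table 1, a subject who stops before Week 12 has no scheduled on-treatment scan and none at the end-of-treatment visit. The request in Section 8.1.12 to document later progression may recover some of them, but it schedules nothing. Table 15 in Appendix 2 puts the first on-treatment scan at Week 9 instead, so the two tables disagree and must be reconciled. On either timing there is a period of about two to three months in which a subject can fail and be left out.

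At stake is a fair reading of two cohorts of up to 16. If one dose loses more subjects early, its denominator shrinks more, and it may look better for that reason alone.

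**Working it through.** **The plan's own figure.** The plan gives no expected ORR and no non-evaluable rate. Its only calculated design is the Simon rule for PSA response in Section 9.1.2: 9 subjects, continue with at least 2 responses; 16 in total, reject with at least 5; null 10%, alternative 40%, one-sided 2.5%, power 80%. The probability of rejection is the sum over x = 2 to 9 of P(X₁ = x) × P(X₂ ≥ 5 − x), with X₁ ~ Bin(9, p) and X₂ ~ Bin(7, p). It is 0.0159 at p = 0.10 and 0.815 at p = 0.40, so the design reproduces. It counts PSA responders, and the ORR denominator appears nowhere in it.

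**Direction.** Let N be the number treated, k the number left out with no post-treatment assessment, and x the number with CR or PR.

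- Planned ORR = x/(N − k). All-treated ORR = x/N.
- Ratio of the two = N/(N − k), which is above 1 whenever k ≥ 1, provided x ≥ 1. If x = 0, both rates are 0.
- For the CR rate, x is the number of CRs. If every responder is a PR, the CR rate is 0 in both sets and nothing is inflated.

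**Size.** N = 16 is the planned cohort size. The values of x and k are assumptions.

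| Left out (k of 16) | Ratio 16/(16 − k) | ORR with x = 5 | Exact 95% CI | ORR with x = 2 |
|---|---|---|---|---|
| 0 | 1.00 | 5/16 = 31.3% | 11.0–58.7% | 12.5% |
| 1 | 1.07 | 5/15 = 33.3% | 11.8–61.6% | 13.3% |
| 2 | 1.14 | 5/14 = 35.7% | 12.8–64.9% | 14.3% |
| 3 | 1.23 | 5/13 = 38.5% | 13.9–68.4% | 15.4% |
| 4 | 1.33 | 5/12 = 41.7% | 15.2–72.3% | 16.7% |

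**Comparison of doses.** Take two doses that each have 5 responders among 16 treated. If one loses 4 failures and the other none, the reported rates are 41.7% and 31.3%, a gap of 10.4 points produced by the denominator alone. The effect does not always reverse the order: a dose with 3 responders that loses 4 failures shows 3/12 = 25%, still below 5/16 = 31%.

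**An opposite pull.** Inclusion criterion 6 admits subjects with evaluable bone disease only. Appendix 2 says bone lesions are not to be recorded as target or nontarget lesions, so these subjects cannot reach CR or PR in Tables 13 and 14, yet they stay in the denominator once assessed. Suppose 4 of 16 are bone-only, 2 soft-tissue failures are left out and 5 subjects respond. The planned ORR is then 5/14 = 36%, the all-treated ORR 5/16 = 31%, and the ORR among treated subjects with soft-tissue disease 5/(16 − 4) = 5/12 = 42%.

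**The case against.** The strongest reply is that few subjects may be affected and little depends on the rates. Section 9.2 does not define a disease assessment. Section 8.2 includes clinical examination in extra-skeletal assessment, and Section 8.1.2 schedules targeted examinations at each visit, so on a broad reading few subjects would be excluded. No decision rule uses ORR or CR rate. Disposition is tabulated (Section 9.4) and all data are listed by subject (Section 9.8), so a reader could rebuild the all-treated rate. PFS runs from first dose and is not restricted to the efficacy-evaluable set. Even at 4 of 16 left out, the intervals (11–59% and 15–72%) overlap heavily.

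All of this limits the consequence, and it stands. It does not change the direction. A broader reading would reduce k, but the express exclusion of undocumented clinical progression would remain. A rate that readers must rebuild from listings is not the rate that will be quoted.

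One could also say that the separate SAP will settle it. Section 9.4 does defer further detail to a SAP that is not among the documents. Section 9.5.4, however, defers only the censoring rules for DOR and PFS; it fixes the denominators of ORR and CR rate itself.

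**Conclusion.** The point holds as a question of denominator and should be fixed. Compared with all treated subjects, the planned ORR can only be raised by leaving out unassessed subjects, by the factor N/(N − k). With an assumed 5 responders of 16, that means 31% becomes 36% with 2 left out and 42% with 4. The true size is unknown because the documents give no non-evaluable rate.

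Three stronger readings are tempting, and the documents do not support them:

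- A reader might infer that the CR rate is always inflated as well. It is not unless there is at least one CR.
- A reader might infer that the dose with more early failures must show the better rate. That can happen when responder counts are equal or close; the example of 25% against 31% shows that it is not general.
- A reader might infer that the Phase 2 efficacy test is compromised. The Simon rule counts PSA responses, and the denominator in Section 9.5.4 does not enter it. Its type I error of 1.6% and power of 81.5% do not depend on this choice.

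Nor does the point show that the planned ORR overstates activity in subjects able to respond, because bone-only subjects pull the figure the other way. These are two separate distortions, and they cannot be relied on to cancel.

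**What to change.** In Sections 9.2 and 9.5.4:

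1. Make the primary denominator for ORR and CR rate all subjects in the dose cohort who receive at least one dose of ONCT-534, and state that those with no post-treatment disease assessment count as non-responders.
2. Keep the efficacy-evaluable set as a sensitivity analysis.
3. Also report ORR among treated subjects with soft-tissue disease at baseline, because bone-only subjects cannot reach CR or PR.
4. Reconcile the first on-treatment scan in Table 1 (Week 12) with that in Table 15 (Week 9), so that it is clear when a subject first becomes assessable.

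The cost is small. It is a change of wording in the protocol and SAP. The efficacy-evaluable results already planned stay as the sensitivity analysis, all-treated results lead, and the soft-tissue ORR needs one further table row. No extra data are collected. The downside is a slightly lower reported rate, and an all-treated ORR that includes subjects who cannot respond by these criteria, which is the reason for the third item.
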